10.12 Schedule of study activities

Day of Study	Event/Activity	Forms to be completed (Annex)
Day 0	Screening/Enrollment/Vaccination	Screening Form Enrollment Survey Vaccination Form
Day 3	Day 3 Post-Vaccination Follow-up	Day 3 Post Vaccination Follow-up Form
Day 7	Day 7 Post-Vaccination Follow-up	Day 7 Post Vaccination Follow-up Form
Day 28	Day 28 Post-Vaccination Follow-up/blood sample collection	Day 28 Blood collection Form
End of Season	End of Season Survey/blood sample collection	End of Season Survey

10.13 Study outcomes

The primary outcome to be measured will be seroconversion at day 28 after vaccination. Seroconversion will be defined as having a haemagglutination inhibition (HI) geometric mean titre (GMT) of \geq 1:40 in the case the pre-vaccination HI GMT <1:10 or having a four-fold rise in titre in the case the pre-vaccination HI GMT \geq 1:10. We will also measure HI GMT at the end of season. Seroprotection will be defined as having an HI GMT \geq 1:40.

Other outcomes that will be measured include:

-reactogenicity to vaccination

-acceptability of AD influenza vaccination

-acute respiratory illness (ARI)

-ARI-associated outcomes (absenteeism, medical visits, hospitalization, other)

-laboratory-confirmed influenza and other respiratory pathogens

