In the Americas, health authorities recommend that HCP receive annual influenza vaccination [18] to protect them from influenza illness, its potentially serious complications, and associated absenteeism, as well as to limit contagion from providers to their frequently vulnerable patient population. As such, HCPs frequently receive annual vaccinations and a substantive proportion of them might have attenuated or no response to additional standard dose influenza vaccines. In this population that is seasonally exposed to influenza illnesses and repeatedly vaccinated using SD vaccines [19, 20], AD vaccines might elicit a better immunity than the typically used SD. We therefore propose to conduct a double-blinded randomized controlled vaccine trial among HCPs to determine if AD influenza vaccines generate superior seroprotection against influenza than SD vaccines particularly among previous sub-optimal responders.

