10.2 Sample size

We calculate that we will need a minimum sample size of 118 participants per vaccination group for detecting a difference between two proportions (based on seroprotection percentages for influenza A(H1N1p) of a previous study:91% vs 78% [21]) (see below), considering a 95% confidence level (two-sided) and 80% statistical power. To account for loss to follow up, we will increase sample size by 20%, so sample size will be a minimum of 142 subjects per group (Table 1).

Table 1. Sample size calculation based on published seroprotection rates for different influenza viruses

Seroprotection	P1 (AD group)	P2 (SD group)	n/per group	With additional 20%
subtypes				
Influenza A(H1N1p)	91%	78%	118	142
Influenza A(H3N2)	No information	No information		

Influenza B	No information	No information		
Where P1=percentage o	f seroprotection for AD g	roup and P2=percentage	e of seroprotection for S	D group

However, although the sample size calculation yields 142 participants per group, there may be different scenarios in which the difference between groups is shortened. In the following table, differences of 10-20% are estimated (Table 2). As a result of this calculation, it is estimated that a sample size of approximately 400 individuals per group will allow us to detect a difference of at least 10% considering a 78% seroprotection rate in the group vaccinated with non-adjuvant vaccine.

Table 2. Different scenarios in seroprotection rates (28 days post-vaccination) per group and sample size calculation

Seroprotection rate in SD group	Relative increase (5) in AD group vs SD group	n per group	Total n	With additional 20%
78%	10%	359	718	862
78%	20%	70	140	168
88g%	10%	131	262	314
88%	15%	58	116	140

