11. ANALYSIS

11.1 Data analysis

Baseline data will be described and analyzed for group comparison, as a check on the adequacy of randomization procedures. Table 3 includes the dependent variables for the primary objective and the first 4 secondary objectives, including the evaluation criteria for each one (Table 3), while tables 4 and 5 detail the dependent variables for secondary objectives 5 and 6, accordingly.

Primary objective: To determine if AD influenza vaccine generates superior immunogenicity than the nonadjuvanted SD influenza vaccine, at approximately 28 days after vaccination and at the end of season, among HCP.

				Criterios de	Tipo de	Instrumento de
	Dimensión	Indicador	Valores	medición	variable/indicador	medición
Variable	(Dimension)	(Indicator)	(Values)	(Measurement criteria)	(Type of variable/indicator)	(Measurement instrument)
Immunogenicity of AD and SD vaccines among health care workers	Seroconversion (Clinical)	Comparison of HI [*] GMT [†] of serum collected at Day 28 (post- vaccination specimen) and at the end of the influenza season (end of season specimen) to serum collected at Day 0 (pre- vaccination specimen) for each vaccine (AD and SD)	Person seroconverted following vaccination Person did not seroconvert following vaccination	Post- vaccination/end of season HI GMT \geq 1:40 if pre-vaccination HI GMT <1:10 OR 4-fold rise in post- vaccination/end of season HI GMT if pre- vaccination HI GMT \geq 1:10 Post- vaccination/end of season HI GMT <1:40 if pre-vaccination HI GMT <1:10 OR <4-fold rise in post- vaccination/end of season HI GMT if pre- vaccination HI GMT \geq 1:10	Quantitative Continuous	Haemagglutination inhibition assay (laboratory)
	Seroprotection (Clinical)		Person is seroprotected following vaccination	Post- vaccination/end of season HI GMT ≥1:40	Quantitative Continuous	Haemagglutination inhibition assay
			Person is not seroprotected	Post- vaccination/end of season		

	following	HI GMT <1:40	
	vaccination		

*HI = haemagglutination inhibition

[†]GMT = geometric mean titer

Secondary Objective 5: To evaluate laboratory-confirmed influenza illness rates in the group receiving AD influenza vaccination compared to the group receiving SD influenza vaccination.

Variable	Dimensión	Indicador	Valores	Criterios de medición	Tipo de variable/indicador	Instrumento de medición
	(Dimension)	(Indicator)	(Values)	(Measurement criteria)	(Type of variable/indicator)	(Measurement instrument)

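### Seroprotection is scored without the Day-0 titre, so in a repeatedly vaccinated cohort the all-participant comparison of AD with SD may be diluted by prior immunity; a comparison using the Day-0 titre should be pre-specified alongside it

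*Combined protocol and SAP*

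**What the plan says.** Section 10.13 names the primary outcome: "The primary outcome to be measured will be seroconversion at day 28 after vaccination". Seroconversion uses the Day-0 titre: it requires 1:40 from a start below 1:10, or a four-fold rise from 1:10 or more. Seroprotection is defined differently: "Seroprotection will be defined as having an HI GMT \geq 1:40". The variables table in section 11.1 has the category "Person is seroprotected following vaccination" and scores it from the post-vaccination or end-of-season titre alone.

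Under the primary objective, section 11.1 compares GMT, seroconversion and seroprotection between the arms in all trial participants. The summary table assigns the primary analysis to the per-protocol population, defined as everyone vaccinated. Neither population is limited by Day-0 titre. The covariates listed for secondary objectives 3 and 4 do not include Day-0 titre.

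Section 8 describes the cohort: "In this population that is seasonally exposed to influenza illnesses and repeatedly vaccinated using SD vaccines". It then frames the trial's question as superior seroprotection. The sample size in section 10.2 is "based on seroprotection percentages for influenza A(H1N1p) of a previous study:91% vs 78" per cent. Table 2 of that section adds a scenario of 78% in the SD group with a 10% relative increase, and this scenario supports about 400 per group.

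**The concern.** A participant who starts at 1:40 or more and stays there adds a success to either arm and says nothing about the adjuvant. The more such participants there are, the less of the seroprotection comparison concerns people whose status the vaccine could change. Prior infection and the number of prior vaccinations are examined as secondary objectives, but neither is the Day-0 titre.

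What is at stake is how the result is read. If the arms show similar seroprotection, the planned output cannot distinguish a lack of adjuvant benefit from a cohort that was mostly protected beforehand. The Day-0 serum that would separate the two is drawn from everyone.

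**Working it through.** **1. The plan's own figures.** Inputs from section 10.2: two-sided 5%, 80% power, 91% vs 78%, and 78% with a 10% relative increase (0.78 × 1.10 = 85.8%). The unpooled formula n = (1.960 + 0.842)² × [p₁(1−p₁) + p₂(1−p₂)] / (p₁−p₂)² gives:
- 91% vs 78%: 7.849 × 0.2535 / 0.0169 = 117.7, so 118 as stated; 118 × 1.2 = 141.6, so 142 as stated.
- 86% vs 78% (85.8% rounded): 7.849 × 0.2920 / 0.0064 = 358.1, so 359 as stated.

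The plan's arithmetic reproduces.

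**2. Assumptions for the check.** Let s be the share at 1:40 or more on Day 0. The documents do not give it, so 0.3, 0.5 and 0.7 are used. Assume these participants stay at 1:40 or more, and take 400 evaluable per group. Power for a two-sided two-proportion test is Φ{[d − 1.96√(2p̄(1−p̄)/n)] / √([p₁(1−p₁) + p₂(1−p₂)]/n)}, where d = p₁−p₂ and p̄ is the mean of the two rates. For 85.8% vs 78% with n = 400 this is Φ{(0.0780 − 0.0534)/0.0271} = 82%.

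**3. Reading A: 78% and 85.8% are rates in all participants.** This is how section 10.2 words them. The all-participant power is then 82% whatever s is. Among those below 1:40 on Day 0, each arm's rate is (p − s)/(1 − s) and n is 400(1 − s).

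| s | n per group | SD | AD | Gap (points) | Power, restricted | Power, all |
|---|---|---|---|---|---|---|
| 0.3 | 280 | 68.6% | 79.7% | 11.1 | 86% | 82% |
| 0.5 | 200 | 56.0% | 71.6% | 15.6 | 90% | 82% |
| 0.7 | 120 | 26.7% | 52.7% | 26.0 | 99% | 82% |

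With 320 evaluable per group (400 less 20%), the same formulas give 77%, 83% and 96% for the restricted comparison, against 73% for all.

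**4. Reading B: the same rates hold only below 1:40 on Day 0.** Each all-participant rate is s + (1 − s)p, so the gap is (1 − s) × 7.8 points.

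| s | Gap, all (points) | Power, all (n = 400) | Power, restricted (n = 400(1 − s)) |
|---|---|---|---|
| 0.3 | 5.5 | 64% | 67% |
| 0.5 | 3.9 | 49% | 53% |
| 0.7 | 2.3 | 31% | 35% |

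The restricted comparison gains about 3 to 4 points here, and about 1 point at s = 0.1 (77% to 78%). For 91% vs 78%, reading B gives all-participant power of 99%, 93% and 75% at these shares, and 80% is kept up to s of about 0.66.

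**5. Between the readings.** If the cited study had its own Day-0 share s₀, with the same response below 1:40, the 13-point gap becomes 13 × (1 − s)/(1 − s₀). With s = s₀ = 0.2 it stays at 13.0. With s₀ = 0.2 and s = 0.4 it is 9.75. With s₀ = 0 and s = 0.4 it is 7.8. The documents do not give s₀.

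**The case against.** The strongest reply is that the plan already deals with prior immunity. The primary outcome is seroconversion, which uses the Day-0 titre. On the two-fold dilution scale it amounts to reaching 1:40 for anyone starting below 1:10 or at 1:10; among titres below 1:40, only a start at 1:20 is treated differently. GMT is also compared, randomisation balances Day-0 titres in expectation, and the share of all HCP at 1:40 or more is a legitimate quantity for vaccination policy. All of this stands. It is why the all-participant comparison should be kept, and why the point concerns precision and interpretation. It does not supply a seroprotection comparison in those whose status can change, and seroprotection is tested under the primary objective.

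A reader might infer more: that the assumed gap shrinks in proportion to the Day-0 share, so that about 400 per group cannot detect the Table 2 difference. The documents do not support this. Section 10.2 gives 78% as the rate in the whole SD group at Day 28, which already includes anyone protected at the start. Nothing says that 78% and 91% describe people below 1:40, and the title of the cited study in the reference list does not settle it. Nor does every HCP at 1:40 or more on Day 0 necessarily count as a success. Some may fall below, particularly by the end of the season.

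It can also be said that restriction hardly helps. That is true only under reading B.

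**Conclusion.** The point holds as a matter of dilution and interpretability. Seroprotection has no Day-0 term, the analysis neither restricts nor adjusts for Day-0 titre, and the cohort is one in which prior titres at 1:40 or more are plausible. There is no bias between arms, and seroconversion is untouched.

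The size depends on a Day-0 share that the documents do not give and on which population the planning rates describe. Under the plan's whole-group wording, the restricted comparison raises power from 82% to about 86%, 90% and 99% at shares of 0.3, 0.5 and 0.7. If the rates hold only below 1:40, the gain is about 1 to 4 points, and only then does the all-participant gap shrink by the full Day-0 share. Both sets of figures assume 400 evaluable per group and that those protected on Day 0 stay protected, which is less certain at the end of the season than at Day 28. Under either reading, the restricted comparison shows the effect in the people the vaccine can move.

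**What to change.** In section 11.1:
- Keep the all-participant seroprotection comparison.
- Pre-specify alongside it the AD-SD comparison among HCP with a Day-0 titre below 1:40 for the strain in question, or an all-participant comparison adjusted for Day-0 log titre.
- Report the share at 1:40 or more on Day 0, by arm and strain.

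In section 10.2, state as an assumption which population the 78% and 91% describe. Do not assert that they refer to HCP below 1:40 on Day 0. If that is the assumption chosen, show the all-participant gap and power over a range of Day-0 shares.

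The cost is wording. Day-0 serum is drawn from every participant before vaccination, so the titre cannot be affected by the vaccine and restricting on it preserves the randomised comparison. The small downside is fewer participants in the restricted comparison, with a different subset for each strain, and one more analysis to report.

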11. ANALYSIS

11.1 Data analysis

Baseline data will be described and analyzed for group comparison, as a check on the adequacy of randomization procedures. Table 3 includes the dependent variables for the primary objective and the first 4 secondary objectives, including the evaluation criteria for each one (Table 3), while tables 4 and 5 detail the dependent variables for secondary objectives 5 and 6, accordingly.

Primary objective: To determine if AD influenza vaccine generates superior immunogenicity than the nonadjuvanted SD influenza vaccine, at approximately 28 days after vaccination and at the end of season, among HCP.

				Criterios de	Tipo de	Instrumento de
	Dimensión	Indicador	Valores	medición	variable/indicador	medición
Variable	(Dimension)	(Indicator)	(Values)	(Measurement criteria)	(Type of variable/indicator)	(Measurement instrument)
Immunogenicity of AD and SD vaccines among health care workers	Seroconversion (Clinical)	Comparison of HI [*] GMT [†] of serum collected at Day 28 (post- vaccination specimen) and at the end of the influenza season (end of season specimen) to serum collected at Day 0 (pre- vaccination specimen) for each vaccine (AD and SD)	Person seroconverted following vaccination Person did not seroconvert following vaccination	Post- vaccination/end of season HI GMT \geq 1:40 if pre-vaccination HI GMT <1:10 OR 4-fold rise in post- vaccination/end of season HI GMT if pre- vaccination HI GMT \geq 1:10 Post- vaccination/end of season HI GMT <1:40 if pre-vaccination HI GMT <1:10 OR <4-fold rise in post- vaccination/end of season HI GMT if pre- vaccination HI GMT \geq 1:10	Quantitative Continuous	Haemagglutination inhibition assay (laboratory)
	Seroprotection (Clinical)		Person is seroprotected following vaccination	Post- vaccination/end of season HI GMT ≥1:40	Quantitative Continuous	Haemagglutination inhibition assay
			Person is not seroprotected	Post- vaccination/end of season		

	following	HI GMT <1:40	
	vaccination		

*HI = haemagglutination inhibition

[†]GMT = geometric mean titer

Secondary Objective 5: To evaluate laboratory-confirmed influenza illness rates in the group receiving AD influenza vaccination compared to the group receiving SD influenza vaccination.

Variable	Dimensión	Indicador	Valores	Criterios de medición	Tipo de variable/indicador	Instrumento de medición
	(Dimension)	(Indicator)	(Values)	(Measurement criteria)	(Type of variable/indicator)	(Measurement instrument)
Laboratory- confirmed influenza illness rates in HCP receiving AD	Clinical	Comparison of persons who did and did not become sick with influenza after receiving the AD or SD	Person became sick with influenza after receiving AD or SD vaccine Person did not become	Nasal swab specimen tests positive for influenza by PCR	Quantitative Discrete	PCR assay (laboratory)
vaccine		vaccine	sick with influenza after receiving AD or SD vaccine	Nasal swab specimen tests negative for influenza by PCR		

Secondary Objective 6: To assess the adverse events among HCP receiving SD and AD influenza vaccines

				Criterios de	Tipo de	Instrumento de
Variable	Dimensión	Indicador	Valores	medición	variable/indicador	medición
	(Dimension)	(Indicator)	(Values)	(Measurement criteria)	(Type of variable/indicator)	(Measurement instrument)
Adverse events in HCP receiving AD vs. SD vaccine	Anticipated (Clinical)	Local reactions: pain on vaccination site, swelling, lump itching, bruising	Yes	Person had a local and/or systemic reaction(s) after receiving AD or SD vaccine	Quantitative Discrete	Post-vaccination surveillance via follow-up visits and monitoring (calls, surveys)

	AND/OR Systemic reactions: fever (≥38°C), muscle ache, joint pain, headache, malaise, fatigue, weakness, sweating, shivering	No	Person did not have a local and/or systemic reaction(s) after receiving AD or SD vaccine		
	Death, life- threatening adverse event, hospitalization or prolongation of existing	Yes	Person had a serious adverse event after receiving the AD or SD vaccine		Post-vaccination surveillance via
Serious, Unanticipated (Clinical)	hospitalization, a persistent or significant incapacity affecting normal life activities, and other unanticipated event that seriously impacts the health of participants	No	Person did not have a serious adverse event after receiving the AD or SD vaccine	Quantitative Discrete	follow-up visits, monitoring (calls, surveys), and hospitalizations

Below we describe the statistical tests that we will perform to address each primary and secondary objective, highlighting which study population will be included for each analysis. All statistical tests will be performed with a significance level of 5% and a statistical power of 80%.

Primary objective: To determine if AD influenza vaccine generates superior immunogenicity than the nonadjuvanted SD influenza vaccine, at approximately 28 days after vaccination and at the end of season, among HCP. We will use Wilcoxon signed-rank tests to assess HI GMT differences and differences in proportions of HCP who seroconverted and were seroprotected between AD and SD vaccination groups. All HCP included in the clinical trial will be included as the study population for these analyses.

Secondary objectives:

1) To compare immune responses post-vaccination, at approximately 28 days after vaccination and at the end of season, among HCP with a history of PCR-confirmed influenza infection during any of the six cohort years (2016 to 2021). The outcome variables will be the same as those of the primary objective matrix of variables, but dividing the enrolled study population to include only the HCP with a history of PCR-confirmed influenza infection during any of the six-year cohort (2016-2021). We will use Wilcoxon signed-rank tests to assess HI GMT differences and differences in proportions of HCP who seroconverted and were seroprotected between AD and SD vaccination groups. Only HCP in the clinical trial with a history of PCR-confirmed influenza infection during any of the six cohort years (2016 to 2021) will be included as the study population for these analyses.

2) To compare immune responses post-vaccination, at approximately 28 days after vaccination and at the end of season, among HCP with no history of PCR-confirmed influenza infection during the six cohort years (2016 to 2021), among those with data available for the six cohort years. The outcome variables will be the same as those of the matrix of variables in the primary objective, but dividing the enrolled study population to include only the HCP with no history of PCR-confirmed influenza infection during any of the six-year cohort (2016-2021). We will use Wilcoxon signed-rank tests to assess HI GMT differences and differences in proportions of HCP who seroconverted and were seroprotected between AD and SD vaccination groups. Only HCP in the clinical trial with no history of PCR-confirmed influenza infection during any of the six cohort years (2016 to 2021) will be included as the study population for these analyses.

3) To examine whether the number of prior influenza vaccination during the preceding 10 years, as documented by medical records, modifies immune responses after receipt of vaccination with AD or SD influenza vaccine, at approximately 28 days after vaccination and at the end of season. The result variables will be the same as those of the matrix of variables in the main objective, examining the differences by the number of influenza vaccines received by health personnel (HCP) during the previous 10 years. We will evaluate the possible effects of repeat vaccination on the immunogenicity of AD and SD using multivariate logistic regression models. Other variables to consider in the model include age, sex, presence of chronic diseases, body mass index, smoking, and alcohol consumption due to possible confounding factors with the immune system's response to vaccination against HIV. influenza. All health personnel participating in the clinical trial will be included as a study population for these analyzes.

4) To analyze and identify risk factors for sub-optimal response (lack of seroconversion/seroprotection) to SD and/or AD influenza vaccines. The outcome variables will be the same as those of the matrix of variables in the main objective, examining the differences by the following variables: age (subdivided between age groups: 18-49 years, 50-65 years,> 65 years); sex (man, woman); presence of chronic conditions (diabetes, autoimmune disorder, asthma, blood disorder, chronic lung disease, cardiovascular disease, high blood pressure, HIV / AIDS, kidney disorder, liver disorder, metabolic disorder, neurological disorder); body mass index; smoking and alcohol consumption; previous laboratory confirmed influenza diagnosis; previous influenza vaccine. We will use generalized linear models (GLM) with Poisson or binomial link functions as appropriate to assess risk factors. Other variables to consider in the model include age, sex, presence of chronic diseases, body mass index, smoking, and alcohol consumption due to possible confounding factors with the immune system response to vaccination against HIV. influenza. All health personnel participating in the clinical trial will be included as a study population for these analyzes.

5) To evaluate laboratory-confirmed influenza illness rates in the group receiving AD influenza vaccination compared to the group receiving SD influenza vaccination. Using data collected through active surveillance, we will calculate incidence densities and use descriptive statistics and Z-test to assess differences in the proportion of HCPs who had laboratory-confirmed influenza (as determined by PCR on nasal swab samples) during the period of the clinical trial among the HCP who received the influenza vaccines AD vs. SD. A Cox regression model will be used to adjust the risk of developing influenza between both groups according to demographic and occupational characteristics. Health personnel participating in the clinical trial will be included as a study population for these analyzes.

6) To assess the adverse events among HCP receiving SD and AD influenza vaccines. Using data collected through active surveillance, we will use descriptive statistics and the Z test to assess the differences in the proportions of adverse events (anticipated and serious) between the HCP who received the AD and SD

influenza vaccines. All health personnel participating in the clinical trial will be included as a study population for these analyzes.

Table 1: Summary of Analysis by Endpoints and Analysis Populations.

OBJECTIVE	VALUATION CRITERIA	STATISTICAL TEST	POPULATION OF ANALYSIS
Primary Efficacy Analysis			
To determine if the AD influenza vaccine generates superior immunogenicity than the vaccine against SD influence without adjuvant among the HCP.	Immunogenicity - superior serumconversion of AD vaccine versus SD vaccine in HCP.	Wilcoxon signed rank test.	PP population
Secondary Efficacy Analysis			
To compare the post-vaccine immune response, in approximately 28 days after vaccination and at the end of the influenza season, among the HCP with a history of influenza infection confirmed by PCR result during any of the 6 years during the previous cohort study (2016 to 2021).	Post-vaccination immune responses, approximately 28 days after vaccination and at the end of the season, among HCPs with a history of PCR-confirmed influenza infection	Wilcoxon signed rank test.	ITTm1
To compare the post-vaccine immune response, in approximately 28 days after vaccination and at the end of the influenza season, among the HCP who did not have a history of influenza infection confirmed by PCR result during any of the 6 years during the previous cohort study (2016 to 2021); among those with information available during the 6- year cohort.	Post-vaccination immune responses, at approximately 28 days after vaccination and at the end of the season, among HCPs with no history of PCR- confirmed influenza infection.	Wilcoxon signed rank test.	ITTm2
Examine whether the number of prior vaccinations against influenza during the previous 10 years, as documented in the medical records, modifies the immune response after receiving the AD or SD vaccine in approximately 28 days after vaccination and at the end of flu season.	Immune responses after receiving the AD or SD influenza vaccine, approximately 28 days after vaccination and at the end of the season	Descriptive statistics: multivariable logistic regression model	ITTm
Analyze and identify risk factors for a suboptimal response (lack of seroconversion / sero protection) to standard dose (SD) and / or adjuvanted (AD) influenza vaccines	Risk factors for suboptimal response (lack of seroconversion / seroprotection)	Descriptive statistics. Generalized linear models (GLM) with Poisson or binomial functions as appropriate	ITTm

To assess rates of laboratory-confirmed influenza illness in the group that received the AD adjuvanted influenza vaccine compared to the group that received the standard dose SD influenza vaccine.	Laboratory confirmed influenza illness rates among HCP receiving influenza vaccines AD vs. SD	Descriptive statistics., Calculation of incidence densities. Multivariate Cox Regression Model.	ITTm
Security Analysis			
To assess adverse events among HCP who received SD and	Frequency of AE	Descriptive statistics and	Security
AD influenza vaccines		Z test to evaluate	Population
		differences in	
		proportions	

- Population by Protocol: All HCPs vaccinated with any of the research products.
- ITTm population: HCPs who, having been vaccinated, became ill and did not become ill with influenza after receiving the AD or SD vaccine.
- ITTm1 population: HCPs may, having been vaccinated, became ill with influenza after receiving the AD or SD vaccine at approximately 28 days after vaccination and at the end of the season.
- ITTm2 population: HCPs who, having been vaccinated, did not become ill with influenza after receiving the AD or SD vaccine at approximately 28 days after vaccination and at the end of the season.
- Safety population: HCPs that were vaccinated with the investigational product

